### 3 Study Design

#### 3.1 General Design

- 1) Total number of subjects/Total sample size: Approximately 120 patients with ADHD (with the final number of subjects depending on the proportion of ADHD subjects who have SCT; we have based our projections on an estimated 50% prevalence) in the phenotype phase (screening visit); 50 adults with ADHD and SCT+ will enter the treatment phase with LDX and placebo. We will analyze data from all subjects who take at least one dose of medication in both blocks. Using a 20% drop-out rate to occur throughout the trial, we estimate that approximately 50 subjects will enroll in the trial; 46 patients will complete the first phase of treatment, 44 patients will complete the intervening placebo washout, and 40 patients will complete each treatment phase.
- 2) Justification for sample size: We will enroll a sufficient number of subjects to recruit 80 patients with ADHD and SCT to enter the treatment study. The 50% prevalence of SCT in adult ADHD has been established in community samples [1, 2]. Power for this study was calculated using PASS [22] based on the primary outcome, i.e. change between baseline and week 4 of treatment on the Barkley SCT scale. Previous studies suggest that the upper bound of the effect size for the comparison of ADHD

CONFIDENTIAL

medications vs. placebo for ADHD symptoms varies between 1.2 and 1.5 standard deviations. Using a conservative estimate of effect that is half as robust for SCT as ADHD we based on our calculations on a 0.6 ES for SCT symptoms. The primary comparison will be a reduction in SCT symptoms on LDX vs. placebo. With 45 evaluable patients with SCT we will have 80% power to detect an effect size (ES) of 0.6 using a two-sided test with a type I error of 0.05.

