## 7.2 Statistical Methods

Phenotype Phase: Comparisons between the adult ADHD patients cohorts with SCT and without SCT in terms of ADHD symptoms (total, inattentive and hyperactive-impulsive, symptoms of executive function (BRIEF GEC, metacognition, behavioral regulation scales and subscales: Inhibit, Shift, Emotional Control, Initiate, Working Memory, Plan/Organize, Organization of Materials, Monitor), neuropsychological tests (CANTAB ADHD module, WAIS Coding and Symbol Search and Attention Network Test (ANT), and impairment (on Barkley Functional Impairment Scale (BFIS)) will be examine via One Way ANOVA .

Treatment Phase: Changes in outcome ratings in the patients in the treatment phase with LDX and placebo will be modeled with longitudinal generalized estimating equation (GEE) mixed regression models using STATA 12.0 [StataCorp, 2011 #25856] within the framework of the general linear model (GLM). The GLM allows us flexibility in modeling the outcome variable by choosing the appropriate distribution and link function. Each model will predict outcome scores from treatment group (drug vs. placebo), study visit (ordinal predictor), order (drug or placebo first) and the two and three-way interactions among: treatment group, visit, and order. We will first test for order effects and drop effects that are not significant at  $p < .05$ . The visit by treatment interaction indicates if the reduction in symptoms over time significantly differs between drug and placebo. Our primary analyses will be intention

CONFIDENTIAL

[SHIRE SCT s13-01288]  
Version: 03/03/2016

to treat (ITT) but we will explore the data with less conservative per protocol analyses to assure that we do not miss any signals in the data. Because this is a randomized trial, which follows subjects over a short period of time, missing data is not expected to impact our analyses. Should this become an issue, we will impute data using STATA's impute procedure. Using logistic regression, a responder analysis will be conducted using pre-hoc priori criteria for treatment response (30% decreases in total ADHD-RS and Barkley SCT scores). These will be last observation carried forward (LOCF) endpoint models that predict responder status (yes/no) from drug group, order and the drug by order interaction. Baseline symptom scores will be included as covariates.

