Safety Analysis: Variables to be summarized and listed include vital signs, adverse events, clinical laboratory results, ECG readings, and the C-SSRS. All adverse events results will be tabulated in manuscripts along with significance testing using the appropriate general linear model. These models will use LOCF endpoint analyses with terms for drug, order and the drug by order interaction

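### Section 7.2 tests every adverse event with a drug, order and drug-by-order model but names no test type or sparse-event rule; read as logistic with Wald p-values, it gives p near 1 for an event seen only on LDX

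*Combined protocol and SAP*

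**What the plan says.** The Safety Analysis paragraph of section 7.2 applies formal testing to every adverse event: "All adverse events results will be tabulated in manuscripts along with significance testing using the appropriate general linear model". It then fixes the structure: "These models will use LOCF endpoint analyses with terms for drug, order and the drug by order interaction".

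The distribution and link are left open. The Treatment Phase paragraph of the same section explains what the modelling framework is for: "The GLM allows us flexibility in modeling the outcome variable by choosing the appropriate distribution and link function". The other yes/no outcome in section 7.2, treatment response, is analysed by logistic regression with the same three terms: "These will be last observation carried forward (LOCF) endpoint models that predict responder status (yes/no) from drug group, order and the drug by order interaction".

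For the efficacy models there is a rule for simplifying the model ("We will first test for order effects and drop effects that are not significant at" the 5% level). It is not repeated for adverse events. Nothing in section 7.2 says whether p-values are Wald, likelihood-ratio or exact, or what happens when an event does not occur under one treatment.

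**The concern.** For an adverse event coded yes/no in each treatment block, drug, order and their interaction describe four cells: LDX and placebo within each order. The trial is small, so each cell holds about 20 to 25 patients. When neither placebo cell has an event, the LDX-placebo odds ratio is infinite. Software that iterates to a large finite estimate attaches an enormous standard error, and the Wald ratio goes to zero.

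This is an awkward place for a test to fail. Events on drug with none on placebo are the plainest harm signal a small crossover can give, and the table meant for publication would show that pattern beside p = 0.999 or a blank. The p-value would also turn on choices of link, test and coding that the plan does not make, so it is not pre-specified.

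**Working it through.** **Plan's own figure.** There is none to reproduce: the documents state no power, rate or p-value for the adverse-event tests.

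**Inputs**
- Patients entering the crossover: "50 adults with ADHD and SCT+ will enter the treatment phase with LDX and placebo" (section 3.1).
- Attrition (section 3.1): "44 patients will complete the intervening placebo washout", and "40 patients will complete each treatment phase".
- Allocation: block randomisation (section 5.3), ratio not stated. I assume 1:1, so 50/2 = 25 per order at entry and 40/2 = 20 per order completing.
- Adverse-event rates: not given. All rates below are assumptions.
- Every patient contributes to both blocks, and events under the two treatments fall in different patients.

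**Step 1. Event on LDX only.** Model: logit P(event) = a + b·drug + c·order + d·drug×order, 25 per order, LDX events split evenly between orders. For 8 v 0, b is about 22.9 with a standard error of 26,200 (0/1 coding) or 18,500 (centred coding), so |b|/SE is about 0.001 and p = 0.999. Exact McNemar with m discordant patients all in one direction is 2 × 0.5^m:
- m = 8: 2/256 = 0.008
- m = 10: 2/1024 = 0.002

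| Events, LDX v placebo | Wald p, three terms | Wald p, no interaction | LR p, drug + interaction (2 df) | LR p, drug, no interaction | Exact McNemar |
|---|---|---|---|---|---|
| 8 v 0 | 0.999 | 0.999 | 0.003 | 0.0006 | 0.008 |
| 10 v 0 | 0.999 | 0.999 | 0.0006 | 0.0001 | 0.002 |

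With 20 per order the Wald p-values are again 0.999. The fits in the table ignore the pairing, but that is not the cause: a logit GEE on tables with both placebo cells empty gave p between 0.75 and 0.99, or no standard error.

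**Step 2. One empty placebo cell.** 10 v 1, as 5 and 5 on LDX against 1 and 0 on placebo, 25 per order. Exact McNemar is 2 × (1 + 11)/2^11 = 24/2048 = 0.012.

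| How the drug term is tested | p |
|---|---|
| Wald, 0/1 coding, empty cell in the non-reference order | 0.115 |
| Wald, 0/1 coding, empty cell in the reference order | 0.999 |
| Wald, centred coding | 0.999 |
| Wald, interaction removed | 0.019 |
| LR, drug + interaction (2 df) | 0.005 |

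**Step 3. How often cells are empty.** With placebo incidence p and n patients per order, one given placebo cell is empty with probability z = (1 − p)^n. Both are empty with probability z², and at least one with 1 − (1 − z)².

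| p | n | z | Both empty | At least one empty |
|---|---|---|---|---|
| 2% | 25 | 0.603 | 36% | 84% |
| 2% | 20 | 0.668 | 45% | 89% |
| 5% | 25 | 0.277 | 8% | 48% |
| 5% | 20 | 0.358 | 13% | 59% |
| 10% | 25 | 0.072 | 0.5% | 14% |
| 10% | 20 | 0.122 | 1.5% | 23% |

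**Step 4. False-positive rates of the alternatives.** I summed binomial probabilities over all possible tables, with 10% incidence under both treatments, 25 per order, independent blocks and nominal 5%. The 2-df LR test rejects in about 8%, exact McNemar in about 2%, and mid-P McNemar in about 4%.

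The fits were made in statsmodels, not in the STATA 12.0 that the plan names. Whether that program would report a huge standard error or drop observations was not tested.

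**The case against.** The strongest reply is that the plan names neither a logit link nor a Wald test. It asks for an appropriate model, and a competent analyst could choose a likelihood-ratio test or an identity link. On the same data those give usable answers: LR p = 0.003 on 2 df and identity-link p = 0.003 for 8 v 0. This stands, and it makes the failure conditional. It does not remove the point. The plan's framework and its own responder model lead to a logit for a yes/no event, Wald p-values are ordinary regression output, and no fallback is written. On the 10 v 0 data, readings that the text allows run from p = 0.0001 to p = 0.999.

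Three stronger conclusions that a reader might draw are not supported:
- *Any empty cell ruins the drug test.* It does not. Step 2 shows that the result then depends on coding, on which cell is empty, and on whether the interaction is kept.
- *The interaction term is the culprit.* When both placebo cells are empty, the main-effects logit fails equally. The cause is the absence of placebo events.
- *The test has a known, large loss of power.* Any such figure rests on counting every empty cell as non-significant. The documents do not say that, and an LR test from the same model contradicts it.

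Nor would a harm be hidden. Section 7.2 requires adverse events to be summarised, listed and tabulated, so 8 v 0 would be visible, and the withdrawal and monitoring provisions in sections 8.4 to 8.6 do not use these p-values. The documents also do not show that most adverse events are rare on placebo; at 10% incidence both placebo cells are seldom empty.

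**Conclusion.** The point holds in conditional form. Under the natural reading of section 7.2 (logit link, Wald p-values), an event seen on LDX and in neither placebo cell gets p near 1 or no estimate, where an exact paired test gives 0.008 (8 v 0) or 0.002 (10 v 0). With one empty placebo cell the result is unstable rather than always lost: 0.115 or 0.999 for 10 v 1, against 0.012.

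At this sample size the situation is common for events with 2% placebo incidence (both placebo cells empty in 36-45% of cases), less so at 5% (8-13%) and unusual at 10% (about 1%). These frequencies rest on assumed rates, 1:1 orders and all patients contributing to both blocks. The consequence is a misleading or missing p-value beside correct counts. That should be corrected before analysis, but it does not threaten the primary efficacy result.

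**What to change.** In the Safety Analysis paragraph of section 7.2, state for each adverse event:

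1. The number and percentage of patients with at least one occurrence in each treatment block.
2. The within-patient LDX-placebo risk difference with a 95% confidence interval.
3. An exact or mid-P McNemar p-value. A penalised-likelihood (Firth) test is an acceptable alternative: for 10 v 0 at 25 per order its likelihood-ratio p-value is 0.001.

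Keep the drug, order and drug-by-order model only for outcomes with enough events in all four cells, with the threshold written down (for example at least 5 in each) and the link and test type named. An ordinary likelihood-ratio test would also avoid the p near 1, but Step 4 shows it can be liberal with few events.

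The cost is a change of wording and a simpler analysis, with no extra data, visits or patients. The downside is small: the paired test does not adjust for period, and its exact version is somewhat conservative, which mid-P partly relieves. A period-adjusted paired test can be added for common events.

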### 7.3 Subject Population(s) for Analysis

All subjects will be entered into the analysis including:

All-randomized population: Any subject randomized into the study, regardless of whether they received study drug

All-treated population: Any subject randomized into the study that received at least one dose of study drug

Protocol-compliant population: Any subject who was randomized and received the protocol required study drug exposure and required protocol processing

## 8 Safety and Adverse Events

### 8.1 Definitions

#### Unanticipated Problems Involving Risk to Subjects or Others

Any incident, experience, or outcome that meets all of the following criteria:

CONFIDENTIAL

This material is the property of the NYU School of Medicine and Langone Medical Center. Do not disclose or use except as authorized in writing by the study sponsor

- Unexpected in nature, severity, or frequency (i.e. not described in study-related documents such as the IRB-approved protocol or consent form, the investigators brochure, etc.)
- Related or possibly related to participation in the research (i.e. possibly related means there is a reasonable possibility that the incident experience, or outcome may have been caused by the procedures involved in the research).
- Suggests that the research places subjects or others at greater risk of harm (including physical, psychological, economic, or social harm).

### **Adverse Event**

An **adverse event** (AE) is any symptom, sign, illness or experience that develops or worsens in severity during the course of the study. Intercurrent illnesses or injuries should be regarded as adverse events. Abnormal results of diagnostic procedures are considered to be adverse events if the abnormality:

- results in study withdrawal
- is associated with a serious adverse event
- is associated with clinical signs or symptoms
- leads to additional treatment or to further diagnostic tests
- is considered by the investigator to be of clinical significance

### **Serious Adverse Event**

Adverse events are classified as serious or non-serious. A **serious adverse event** is any AE that is:

- fatal
- life-threatening
- requires or prolongs hospital stay
- results in persistent or significant disability or incapacity
- a congenital anomaly or birth defect
- an important medical event

CONFIDENTIAL

Important medical events are those that may not be immediately life threatening, but are clearly of major clinical significance. They may jeopardize the subject and may require intervention to prevent one of the other serious outcomes noted above. For example, drug overdose or abuse, a seizure that did not result in in-patient hospitalization, or intensive treatment of bronchospasm in an emergency department would typically be considered serious.

All adverse events that do not meet any of the criteria for serious should be regarded as **non-serious adverse events**.

### **Adverse Event Reporting Period**

The study period during which adverse events must be reported is normally defined as the period from the initiation of any study procedures to the end of the study treatment follow-up. For this study, the study treatment follow-up is defined as 30 days following the last administration of study treatment.

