### **5.7 Packaging (Pharmacy)**

- Study drug and placebo is supplied in 20mg, 30mg, 40mg, 50mg, 60mg, and 70mg capsules in bottles containing #9 pills each. The bottles will be labeled with Patient's name, study identification number, Study name and NYU IRB number, study drug name, study drug dosage, strength, quantity, directions for usage and physician's name and contact information.
- Study drug will be shipped in bulk # 40 bottles at each shipment.

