## **6 Study Procedures:**

CONFIDENTIAL

This material is the property of the NYU School of Medicine and Langone Medical Center. Do not disclose or use except as authorized in writing by the study sponsor

	Visit 1	Visit 2	Visit 3	Visit 4	Visit 5	Visit 6	Visit 7	Visit 8	Visit9	Visit 10	Visit 11
Study Procedures and Assessments	Week -3-0	Week 0	Week 1	Week 2	Week 3	Week 4	Week 6	Week 7	Week 8	Week 9	Week 10
	Screening	Baseline 1	Treatment (LDX or PBO) 1			EOT 1	End of PBO Washout/ Baseline2	Treatment (LDX or PBO) 2			EOT 2
SCREENING											
Consent	X										
Demographics	X										
M.I.N.I	X										
ACDS v1.2	X										
Medical History	X										
Psychiatric History	X										
Medical Review of Systems	X										
Physical Exam	X										
Hematology, Chemistry, Urinalysis, and UDS	X										
Urine Pregnancy Test	X										
ECG	X										
Review Eligibility	X	X	X								
EFFICACY											
ADHD-RS		X		X	X	X	X	X	X	X	X
Barkley SCT Scale		X		X	X	X	X	X	X	X	X
CGI-S		x		X	X	X	X	X	X	X	X
SAFETY											
Vital Signs		X	X	X	X	X	X	X	X	X	X
C-SSRS		X	X				X	X			X
Concomitant Medications		X	X	X	X	X	X	X	X	X	X
Adverse Events		X	X	X	X	X	X	X	X	X	X
NEUROPSYCHOLOGICAL BATTERY/EXECUTIVE FUNCTIONING											
CANTAB ADHD		x					X	X			X
WAIS-CODING & SYMBOL SEARCH		X					X	X			X
BRIEF-A		X					X	X			X
BFIS		X					X	X			X
ON-TOP		X									
OTHER											
Dose Dispense/ Adjustment			X	X	X	X			X	X	X
Drug Accountability				X	X	X	X	X	X	X	X

CONFIDENTIAL

This material is the property of the NYU School of Medicine and Langone Medical Center. Do not disclose or use except as authorized in writing by the study sponsor

**STUDY VISIT SCHEDULE:** This is a two part study. Patients will sign this consent form and be asked to do the following: Visit the study doctor weekly over a 12-week period, communicate over the phone between visits 6 and 7 and approximately 1 week after visit 10, and follow study instructions. In addition, patients who participate in the second part of the study will be asked to take study drug as instructed at the same time each day. Patient will have their blood drawn once in the study about 10mls will be collected for hematology and blood chemistry.

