## **6.8 Visit 11 End of Treatment 2; Day 70±2 Week 10**

End of treatment will consist of ADHD-RS with prompts, Barkley SCT Scale, BRIEF-A, Barkley Functional Impairment Scale (BFIS), C-SSRS, neuropsychological battery, CGI, vital signs, assessment of adverse events (AE) and concomitant medications (CM). Drug accountability is performed.

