## **6.9 Follow-Up Telephone/End of Study- Visit Day 77±2; Week 11**

Study Coordinator will call the patient to ask how they been feeling since their last visit. We will document any adverse events, concomitant medications.

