## **8.2 Recording of Adverse Events**

At each contact with the subject, the investigator must seek information on adverse events by specific questioning and, as appropriate, by examination. Information on all adverse events should be recorded immediately in the source document, and also in the appropriate adverse event module of the case report form (CRF). All clearly related signs, symptoms, and abnormal diagnostic procedures results should be recorded in the source document (though should be grouped under one diagnosis).

All adverse events occurring during the study period must be recorded. The clinical course of each event should be followed until resolution, stabilization, or until it has been determined that the study treatment or participation is not the cause. Serious adverse events that are still ongoing at the end of the study period must be followed up to determine the final outcome. Any serious adverse event that occurs after the study period and is considered to be possibly related to the study treatment or study participation should be recorded and reported immediately.

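### Adverse event follow-up is set at 30 days after the last dose, but the last scheduled contact comes about 7 days after it, leaving about 23 days with no active questioning

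*Combined protocol and SAP*

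**What the plan says.** **Length of the period.** Section 8.1, Adverse Event Reporting Period, defines it as "the period from the initiation of any study procedures to the end of the study treatment follow-up", and adds for this trial that "the study treatment follow-up is defined as 30 days following the last administration of study treatment".

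**What must be recorded in it.** Section 8.2: "All adverse events occurring during the study period must be recorded". The same section makes direct questioning at each contact the way in which events are found.

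**End of treatment.** Section 6.8 is headed "Visit 11 End of Treatment 2; Day 70±2 Week 10". No section gives the calendar day of the last dose.

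**Last contact.** Section 6.9 is headed "Follow-Up Telephone/End of Study- Visit Day 77±2; Week 11". At that call the "Study Coordinator will call the patient to ask how they been feeling since their last visit", and adverse events and concomitant medications are documented. The procedures table in Section 6 stops at Visit 11.

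**A second timing for the same call.** The visit schedule text under that table has patients "communicate over the phone between visits 6 and 7 and approximately 1 week after visit 10".

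**After the last visit.** The Post-study Adverse Event paragraph in Section 8.1 has the investigator tell patients to report later events that they or their physician think may be related to the study. Unresolved events are followed up. Section 8.2 adds prompt reporting of possibly related serious events that arise after the study period.

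**The concern.** The protocol states a reporting period and a rule of complete recording, and its contact schedule cannot deliver either. A site could make every visit and call on time and still have no planned opportunity to ask about most of the 30 days after treatment. An adverse event table described as running to 30 days after the last dose would then combine actively sought events, up to the call, with whatever patients chose to report afterwards. A reader of that table could not tell the two apart.

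At stake is whether the safety data match the period claimed for them. The primary efficacy analysis is not affected.

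**Working it through.** **Inputs**

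- Post-treatment follow-up: 30 days (Section 8.1).
- Visit 11: Day 70±2, so Day 68 to 72 (Section 6.8).
- Final call: Day 77±2, so Day 75 to 79 (Section 6.9).
- Visit 10: Day 63±2 (Section 6.7).
- Assumption: the last dose falls at about Visit 11, because the documents do not give its day.

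**The plan's own days.** 10 weeks × 7 = Day 70 and 11 weeks × 7 = Day 77, so the stated days and weeks agree.

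**Formulas.** Days covered = day of last contact − day of last dose. Days without scheduled contact = 30 − days covered.

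**Main result.** The period ends at 70 + 30 = Day 100. Days covered = 77 − 70 = 7. Days without contact = 30 − 7 = 23, and 23/30 = 77%.

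**Sensitivity**

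| Scenario | Last dose | Last contact | Covered | Without contact |
|---|---|---|---|---|
| Nominal | Day 70 | Day 77 | 7 | 23 (77%) |
| Windows, shortest gap | Day 72 | Day 75 | 3 | 27 (90%) |
| Windows, longest gap | Day 68 | Day 79 | 11 | 19 (63%) |
| Last dose the day before Visit 11 | Day 69 | Day 77 | 8 | 22 (73%) |
| Visit 10 bottle used up | Day 72 | Day 77 | 5 | 25 (83%) |
| Call timed as in the Section 6 text | Day 70 | Day 70 | 0 | 30 (100%) |

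The fifth row uses Section 5.7, which supplies "capsules in bottles containing #9 pills each". Nine capsules dispensed on Day 63 and started the next morning last from Day 64 to Day 72. The sixth row uses 63 + 7 = Day 70, the day of Visit 11 itself. That wording may be a slip in the visit number, but the documents do not say so.

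The procedures table also appears to mark dispensing at Visit 11, which Section 6.8 does not list. The table columns may have shifted in extraction, so I place no weight on this. If drug were dispensed there for seven more days, the last dose would fall on Day 77 and none of the 30 days would be covered.

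In every row more than half of the 30 days has no scheduled contact.

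**Share of the whole reporting period.** From the earliest screening day (Day −21) to Day 100 is 121 days, and 23/121 = 19%. The shortfall is therefore large within the post-treatment follow-up but modest within the full period.

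**Does passive reporting fill it?** Section 8.2 asks for all events. The Post-study Adverse Event paragraph asks patients only for those thought to be related. Following unresolved events does not detect new ones. The rule on later serious events concerns a time after the study period and a narrower class of event. Unrelated events, and related events that nobody recognises as related, have no planned route into the record from about Day 78 to Day 100.

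**The case against.** The strongest reply is that the period is not unobserved. The protocol provides for later reporting by patients, for notification of the sponsor about later deaths and possibly related events, and for follow-up of unresolved events. This stands, and it limits the point to the absence of scheduled contact and active questioning. It does not remove the contradiction, because that route covers only events believed related while Section 8.2 asks for all.

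A reader might go further and infer that withdrawal effects of the study drug will be under-counted, and only in patients given LDX second. The documents do not support that:

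- The Day 77 call covers about the first week after treatment. The Study Summary itself uses one week as the washout for psychostimulants, and Section 1.6.2 describes effects of stopping similar drugs as temporary. Nothing points to drug-related events gathering in Days 78 to 100.
- Patients given placebo second follow the same schedule and have the same gap.
- Contact after the first block is denser: in the 30 days from Day 28 to Day 58 there are contacts at Days 35, 42, 49 and 56. But by Day 42 the second block has begun, and the protocol does not say to which treatment such events are assigned. The Safety Analysis paragraph in Section 7.2 does not say whether events after the end of treatment enter the models for drug and order.

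It is also fair to object that a contact might be set out in the monitoring plan (Attachment 6), which is not in the supplied text. The claim is therefore that none is scheduled in the text available.

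**Conclusion.** The point holds as an inconsistency between the stated adverse event period and the contact schedule. With the last dose at about Visit 11, about 23 of the 30 post-treatment days (77%) have no scheduled contact. The figure is 19 to 27 days (63% to 90%) when both visit windows are applied, and it reaches 30 if the call is timed as in the Section 6 text. Events that are unrelated, or not recognised as related, may be missed in both sequences, and the stated period is not delivered.

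The conclusion rests on the assumed day of the last dose and on no further contact being scheduled outside the supplied text. It does not extend to bias between LDX and placebo, whose size and direction cannot be derived from these documents. The inconsistency should be corrected, but it does not threaten the primary result.

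**What to change.** Reconcile Section 8.1 (Adverse Event Reporting Period), Section 6.9 and the visit schedule text in Section 6, in one of two ways:

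1. Keep the stated period and align a final telephone contact with its end, asking about all adverse events since the previous contact. Adding a call keeps the Day 77 enquiry; moving the existing call would give it up.
2. State the reporting period that the scheduled contacts cover, and describe anything later as passively reported, in the protocol and in the safety tables.

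The choice is the sponsor's. Either way, give one timing for the final call, state the day of the last dose from which the period is counted, and give a follow-up day for early withdrawals, since Section 4.4.1 has none.

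Cost: the first option needs one moved or added call per patient and a later last contact. The second needs a sentence and a shorter stated period.
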